Effectiveness of virtual reality Situation-Based Flipped Learning and Gamification on nursing students' learning attitudes, problem-solving abilities, and empathetic abilities.

IRB00013623

Date of document: 10-1-2024

The integration of innovative educational approaches in nursing education has become increasingly crucial for enhancing learning outcomes. Among these approaches, virtual reality (VR), Situation-Based Flipped Learning, and Gamification have gained attention as promising tools to engage nursing students and promote a deeper understanding of complex concepts. This study aims to investigate the effectiveness of combining these strategies in a virtual reality Situation-Based Flipped Learning environment with elements of Gamification on nursing students' learning attitudes, problem-solving abilities, and empathetic skills. By leveraging these technologies, educators seek to create an immersive and interactive learning experience that not only aligns with the demands of modern education but also addresses the unique challenges faced by nursing students in developing critical competencies. This research explores the potential impact of this integrated approach on nursing education, contributing valuable insights to the ongoing efforts to optimize teaching methodologies for future healthcare professionals.

Aim of the Study

To explore the impact of educational program by using situation-based flipped learning and gamification on nursing students' learning attitudes, problem-solving abilities, and empathetic abilities at the Faculty of Nursing Zagazig University.

Research Hypotheses

1. The students' learning attitude will be improved after participating in situation-based FL with gamification classes.
2. The students' problem-solving abilities will show a significant change after situation based FL classes combined with gamification.
3. There is a significant increase in students' empathetic abilities after completing situation-based FL classes combined with gamification.

Research Design:

A quasi - experimental design was used.

Study Setting:

The study was carried out at the Faculty of Nursing, Zagazig University, Egypt, which includes seven scientific departments namely; Nursing Administration, Psychiatric and Mental Health Nursing, Pediatric Nursing, Community Health Nursing, Maternal and New Born Health Nursing, Medical Surgical Nursing, Community Health Nursing and Geriatric Nursing.

Subjects:

The subjects of the study included fourth year nursing students who enrolled in nursing administration course in the academic year 2022-2023.

Sample Size:

The sample was taken through a proportionate random sampling technique by using a simplified formula $n= N/1+N (e)^2$, provided by Yamane [1]. A 95% confidence level and $P =0.05$ are assumed for Equation. The ideal sample size was 70 students.

Field Work:

The study was carried out for three months from the beginning of January to the end of March 2023, as the following:

Preparatory phase:

It started with reviewing national and international resource of theoretical and empirical literature on the topic of the study using textbooks, articles, magazines, research, and internet search to get a clear image of all parts of the study. The instructional system was based on Dick and Carey's [27] analysis, design, development, implementation, and evaluation model. This model is a systematic approach that analyzes educational needs to find solutions; designs, develops, implements, and evaluates the results. A needs analysis was conducted via a pre-test questionnaire sheet of students' preferred teaching methods and learning activities. The estimated time each student needed to complete each sheet varied between 30-40 minutes. Accordingly, the educational program's objectives were set out and the content was designed.

The design phase: involved preparing the program, which included a weekly schedule and a list of learning activities divided into out-of-class and in-class activities. Students' performance goals were prepared based on a weekly schedule. Various videos and lecture materials for each class were prepared based on previous studies and the literature on FL. The researchers conducted lectures on FL teaching methods to develop instructional and teaching materials.

The development phase: involved developing educational materials on the selected nursing management skills for out- of-class activities by designing teaching objectives, providing prerecorded video lectures, which can be downloaded by mobile technology devices for preview, and design quizzes, questions, and set up scenarios for application exercise. For in-class activities, individual and group discussion regarding the topic ,collecting activity data {quizzes and answer to questions}, students were given Individual Readiness Assurance test, collaborative Readiness Assurance test , in addition, based on the role-play scenarios and demonstrations, the roles of the patient, patient family, head nurse, nurse leader, and the nurse were assigned to each, and nursing intervention was applied during the role-play. Students who participated in this study were provided immediate feedback on their progress, achievement or rewarded with a badge.

The developed situation-based FL combined with gamification were applied during twelve weeks of decision-making skills, problem solving skills, communication skills, motivation skills, and time management skills modules. In particular, the gamification elements of challenge, competition, scaffolding, achievement, and compensation were applied to all out-class, in-class, and deeper-class domains the students participated in.

For example, in the decision-making skills module, for the out of class activity, goal of decision-making was accurately presented, a prerecorded video lecture on decision making with quiz, questions and a situation problem with scenario as an application exercise pre settled up; the students were asked to watch videos, answer quizzes and

analyze the presented people appeared in the presented situational case scenario as patients, nurses and patient family.

for the in class activity, collecting activity data (answer of questions and quizze1), individual and group discussion , students were given Individual Readiness Assurance test, collaborative team Readiness Assurance test , based on the role-play scenarios and demonstrations, the roles of the patient, patient family, and the nurse were assigned to each, and nursing intervention was applied during the role-play. To ensure that the students who participated in this study were compensated, they were provided immediate feedback on their progress or achievement or rewarded with a badge.

Students were able to check their learning effects and progress, and the results were shared on the leader board to encourage users to learn voluntarily, moreover, stimulate student's competitive spirit, the leader board provided the ranking of each team and the records of the opponents.

[figure not shown]
The implementation phase

The planned educational program was implemented across 12 class; these class lasted 20 hours; from which 6 theory (out-of-class activity: two hours for each module;75min MP4 video lectures and 15 min quiz questions, and 30 min situation case were uploaded to mobile phones); and 6 practical class (in-class activity: four hours for each module) were performed. Five modules comprising 75min MP4 video lectures and 15 min five quiz questions, and 30 min situation case were uploaded to mobile phones for the out-of-class activity.

The modules allowed the students to understand and apply communication skills, decision-making skills, problem solving skills, time management skills, and motivation skills in each class. For the out-of-class activity, students were asked to watch skills for each a video lecture and participate in the class. The video presented knowledge about each skill through videos, images, and sound. In-class activity was operated with mini-lectures and team-based learning. The students faced challenges, competition, self-expression, achievements, and rewards during the course, which are gamification elements. It was hard to take the entire number of students at the same time, so the students were distributed into five groups; every group comprised approximately 14 students. All sessions were repeated to the five main groups until the 70 students finished all 15 hours of instruction.

The evaluation phase, the students took the individual readiness assurance test (iRAT) before each class to review the content they had learned while preparing for each class. This was followed by the team readiness assurance test (tRAT), in which they formed teams to discuss, solve, and submit answers to a quiz composed of the same questions as those in the iRAT. After completing the tRAT, the instructor shared the correct answers and gave mini-lectures to explain what the students had not understood. The questions in these situational cases were to be solved through team based cooperative learning and competition. Additionally, after each class, the students wrote in reflection notes as a post-class activity.

Figure 1. Situation-based flipped learning and gamification as combined methodologies on nursing students'

learning attitudes, problem-solving abilities, and empathetic abilities.

Abbreviations: FL: Flipped Learning; iRAT: Individual Readiness Assurance Test.

Tools of data collection:

A questionnaire sheet including 4 parts:

Part (1): Personal characteristics of nursing students developed by the researchers: Age, gender, previous working, and previous training about flipped learning and gamification.

(2): Learning Attitude Scale

Developed by Hwang [28] to evaluate students' attitudes, habits, beliefs, and motivations toward class. The scale consisted of 40 items divided into four subsections; the first (9 items), dealt with the nature of learning, e.g. (the clever ones learn more easily); the second (11 items), with expectations from learning e.g. (learning new things makes me successful in what I do.); the third (10 items), with openness to learning e.g.(I want to develop my communication with people through learning new); and the fourth (10 items), with anxiety about learning, e.g. (I am anxious while being

introduced a new subject). This tool uses a five-point Likert scale (1 = not at all, 5 = very much), and the higher the score, the better the learning attitude. In Hwang's study [28], Cronbach's α was 0.84.

Problem-Solving Ability

Developed by Lee et al. [29] to measure problem-solving ability. It consists of 45 items in five categories and six sub-categories (Clarifying problem, seeking a solution, decision making, applying the solution, and evaluation & reflection). The tool uses a five-point Likert scale (never, rarely, sometimes, often, always), and the higher the score, the higher the problem-solving ability. Cronbach's α was 0.94 while developing this instrument [29], and Cronbach's α was 0.92 in this study.

Empathetic Ability

Empathetic ability was measured using a tool developed by Wakabayashi et al. [30] and validated by Yeo [31] using the Korean version of the Empathy Quotient-Short form. It comprises 11 items on a two-point scale to measure empathy's cognitive, emotional, and social aspects e.g. (I can tune into how someone else feels rapidly and intuitively, & I can easily tell if someone else is interested in or bored by what I am saying). The higher the total score, the higher the empathetic ability. In a study by Yeo [31], Cronbach's α was 0.88, and in this study, Cronbach's α was 0.81.

Ethical Consideration

This study was conducted after obtaining ethical approval from the Faculty of nursing - Zagazig University. The students voluntarily participated in this study. They had opportunities to ask questions and were allowed to refuse to provide information. The researchers explained the purpose and method of the study and obtained written informed consent from the participants before conducting the surveys. The students were treated equally, regardless of whether they participated in the study. Furthermore, they were guaranteed anonymity, and their data were not shared with anyone other than the researchers.

Content Validity:

A self-administered questionnaire was used, after the translation of instrument to Arabic. The content and face validity were established by a jury of experts (5 professors & 4 assistant professors) from academic nursing staff, Zagazig and Cairo Universities. In addition, the content validity of the modules were also assessed by them.

Pilot Study:

To test the questionnaire accuracy and feasibility before using, a pilot study was conducted on 10 percent of the research sample ($n=7$). Those students who were included in the pilot study were removed from the sample analysis. Informed consent has been received from the entire study group for participation in the study, and they have been told that participation in the research is voluntary. And that every student can decide to stop completing the study and withdraw without consequences at any point.

Statistical Design:

Entering data and using statistical evaluation (SPSS), version 21.0. And checked to ensure no information was lost or inadequate. ANOVA F test and t-test were used to identify the relationship between the variables and the analysis of the association between total scores.

References

- 27- Dick,W.; Cary, L. The Systematic Design of Instruction, 4th ed.; Harper Collins College Publishers: New York, NY, USA, 1996.**
- 28- Hwang, S. Problem-Based Learning on the Knowledge Achievement, Critical Thinking Ability, Attitude and Motivation Toward Learning of Nursing Students; Chonnam National University: Gwangju, Korea, 2003.am Readiness Assurance Test**

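### All 70 students get the same content by the same method, and that content includes problem solving, so a gain on the problem-solving hypothesis (H2) cannot be attributed to flipped learning with gamification

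*Protocol*

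**What the plan says.** **Content.** Protocol, Field Work, the development phase: the programme was "applied during twelve weeks of decision-making skills, problem solving skills, communication skills, motivation skills, and time management skills modules". The implementation phase gives the same number, "Five modules comprising 75min MP4 video lectures and 15 min five quiz questions", and presents the skills as subject matter: "The modules allowed the students to understand and apply communication skills, decision-making skills, problem solving skills, time management skills, and motivation skills in each class".

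**Outcome.** Research Hypotheses, item 2 (H2): "The students' problem-solving abilities will show a significant change after situation based FL classes combined with gamification". Under Tools of data collection, the instrument is a 45-item self-rated scale whose named categories are "Clarifying problem, seeking a solution, decision making, applying the solution, and evaluation & reflection".

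**Who receives what.** The implementation phase divides the 70 students into five groups of about 14 and repeats every session for each group. Research Design calls the study quasi-experimental. No comparison group of any kind is described.

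**Claim.** The title speaks of the effectiveness of the teaching approach. The introduction says the study investigates how effective the combination of strategies is, and ends by presenting the research as "contributing valuable insights to the ongoing efforts to optimize teaching methodologies for future healthcare professionals".

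**Analysis.** Statistical Design names an ANOVA F test and a t-test on total scores.

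**The concern.** The title and introduction ask whether a way of teaching works. H2 measures a skill that the programme also teaches directly as a topic. Students taught problem solving and decision making by any competent means, ordinary lectures included, might rate their problem solving higher afterwards. A significant H2 result would then be no specific evidence for flipping or gamifying the classes.

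At stake is the conclusion drawn. Someone choosing a teaching method could take a positive H2 as a reason to adopt this one, when the same result could have come from putting these two topics on the timetable.

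**Working it through.** The protocol gives no figure for this point, so the check sets the passages side by side and asks what the design can identify.

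**1. Overlap of content and outcome**
- Modules taught: decision making, problem solving, communication, motivation, time management = 5.
- Modules matching the H2 scale by name: problem solving (the scale as a whole) and decision making (one category) = 2. Share: 2/5 = 40%.
- Named scale categories carrying a module's name: 1 of 5.
- By time, using the per-module hours in the implementation phase (2 h out of class + 4 h in class = 6 h): 2 × 6 = 12 h of 5 × 6 = 30 h, again 40%. That section also gives totals of 20 h and 15 h, which do not agree with 30 h. This is a separate matter. If the modules are of equal length, the share is 40% under any total.

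**2. Contrast available**
- Five groups × 14 students = 70, the full sample.
- Students receiving both the content and the method: 70 of 70.
- Students receiving the content by another method: none described. Students receiving neither: none described.

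**3. What a gain identifies**

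Write the mean change in the H2 score as D = c + m + i + t, where c is the effect of being taught the content, m that of the method, i their interaction, and t everything else that changes over the period (the rest of the course, maturation, repeat testing).
- Design as described: only the sum D is observed. That is one quantity with four unknown parts.
- Adding an untreated group: the difference between groups is c + m + i. This removes t but still does not separate content from method.
- Adding a group taught the same modules conventionally: the difference is m + i, the effect of the method given this content, provided the groups are otherwise comparable.

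Only the third design addresses the question in the title. The planned F test and t-test cannot recover m from the first, and no later analysis plan could, because the contrast is absent from the data.

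**The case against.** The strongest case on the other side is that the study evaluates a package. The Aim of the Study concerns an educational programme that uses these methods, and H2 says only that abilities "will show a significant change after situation based FL classes combined with gamification". That is a before-after statement, with no claim of superiority over lectures. Teaching a skill and then measuring it is normal in education, and the content is openly described. All of this stands, and it is why the H2 test needs no change. It does not rescue the title and introduction, which go beyond the package to the method.

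A reader might infer more than the documents support:
- **That a gain on H2 would be due to the content.** Nothing shows this. Content, method, both, or time are all possible.
- **That the overlap itself is the flaw.** With a comparator taught the same modules it would be harmless. The cause is the absence of that comparator, so the point belongs beside any comment on the missing control group.
- **That 40% is a measure of bias.** It counts module titles. None of the 45 items is shown, so the overlap at item level cannot be checked.
- **That team-based learning is an undisclosed extra intervention.** The implementation phase states "In-class activity was operated with mini-lectures and team-based learning", and the readiness tests are described as part of the programme. It is a disclosed component.

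It is also fair to say that the closing sentence of the introduction is general and not tied to H2, and that the protocol contains no planned conclusion to edit. The request is therefore limited to the stated aim and to how H2 may be interpreted.

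**Conclusion.** Wrong as written: the design cannot support the inference about method effectiveness that the title and introduction state. Content and method are fully confounded, since all 70 students receive both. For H2, the part of any gain due to the method is not identifiable, and the data put no bound on it. What the study can report is a change in problem-solving score after the whole course.

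This rests on two assumptions. The first is that no same-content comparator exists; none is described. The second is that H2 is assessed as change from before to after the programme, as its wording implies. The conclusion does not depend on the exact degree of overlap between modules and scale items.

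**What to change.** - In the introduction, restate the aim, and wherever H2 is interpreted restate the inference, as: the change in problem-solving score after a nursing-management-skills course that teaches problem solving and decision making and is delivered by flipped learning with gamification.
- Add one sentence: because no group was taught the same modules another way, H2 supports no inference about the teaching method.
- Do not rest the introduction's closing claim about improving teaching methods on H2.
- Leave the H2 test as it is. Field work ran from January to March 2023 and the document is dated 10-1-2024, so the remedy limits interpretation and does not alter the design or the test.

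The cost is a few sentences. The downside is a narrower claim. If the method question is to be answered, a later study would need a comparator taught the same modules conventionally.

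### All 70 students are taught the programme and no comparison group is described, so before-after change cannot support the effectiveness and impact claimed

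*Protocol*

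**What the plan says.** - **Title:** "Effectiveness of virtual reality Situation-Based Flipped Learning and Gamification on nursing" students' attitudes, problem-solving and empathy.
- **Introduction:** "This study aims to investigate the effectiveness of combining these strategies".
- **Aim of the Study:** "To explore the impact of educational program by using situation-based flipped learning and gamification".
- **Research Hypotheses:** each of the three is a change following the classes, with no comparator. The first expects that "learning attitude will be improved after participating in situation-based FL with gamification classes".
- **Research Design:** a single sentence, "A quasi - experimental design was used". It does not say whether there is one group or more.
- **Sample Size:** one sample of 70 students.
- **Field Work:** "The study was carried out for three months from the beginning of January to the end of March 2023".
- **The implementation phase:** the whole sample could not be taught together, "so the students were distributed into five groups; every group comprised approximately 14 students". Then: "All sessions were repeated to the five main groups until the 70 students finished all 15 hours of instruction".
- **Statistical Design:** an ANOVA F test and a t-test are named, without saying what is compared with what.

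**The concern.** The title, introduction and aim ask a causal question: does this way of teaching improve the three outcomes? Answering it requires some view of what the scores would have done without the programme. The design described provides none, because every sampled student receives the same sessions.

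Four other explanations for a change run alongside the programme:

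- background change in fourth-year students over the period;
- other teaching received in the same months;
- answering the same questionnaires a second time;
- favourable self-report on self-administered scales after an engaging course.

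The anonymity promised under Ethical Consideration may reduce the fourth. It does nothing about the other three.

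A significant change would be read as proof that flipped learning with gamification works. The design cannot distinguish that from change that would have happened anyway, and no analysis plan can supply the missing comparison afterwards.

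**Working it through.** **1. Is anyone left for comparison?**

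- Sample: 70 (Sample Size).
- Teaching groups: 5 of about 14 (The implementation phase), and 5 x 14 = 70.
- Students completing the programme: 70 (same section).
- Students remaining: 70 - 70 = 0.

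The protocol describes no usual-teaching, delayed-start or historical group. The five batches receive identical sessions, so an ANOVA or t-test across them would not estimate the effect of the programme.

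**2. What can the hypotheses show?** Each concerns change after the classes. One group measured before and after can address that. It cannot address the further step, in the title, introduction and aim, from change to effectiveness or impact.

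**3. How easily could change without any effect look like success?** The protocol gives no SD, effect size, correlation or expected background change, and it has no figure of its own to reproduce on this point. The following is therefore an illustration under stated assumptions.

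*Assumptions:* programme effect zero; background change d of 0.1, 0.2, 0.3 or 0.4 SD of the change score; two-sided alpha 0.05.

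*Paired t-test:* noncentral t with n - 1 degrees of freedom and noncentrality d x sqrt(n). For example, at n = 70 and d = 0.2 the noncentrality is 0.2 x 8.367 = 1.67. The second row takes the 7 pilot students out of the 70 (70 - 7 = 63), because the Pilot Study section removes them from the analysis without saying whether they were among the 70.

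*Unpaired t-test of pre against post scores:* simulated, 40,000 studies, 70 scores on each occasion, assumed pre-post correlation 0.5, same shifts in SD of change.

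| Proportion significant | d = 0.1 | d = 0.2 | d = 0.3 | d = 0.4 |
|---|---|---|---|---|
| Paired, n = 70 | 13% | 38% | 70% | 91% |
| Paired, n = 63 | 12% | 35% | 65% | 88% |
| Unpaired, n = 70, correlation 0.5 | 3% | 14% | 39% | 71% |

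The unpaired row depends on the assumed correlation. At 0.3 it becomes about 7%, 25%, 56% and 84%; at 0.7, about 0.4%, 3%, 15% and 40%.

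*Smallest observed mean change that is significant in the paired test:* t(0.975, n - 1) / sqrt(n).

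- n = 70: 1.995 / 8.367 = 0.24 SD of change.
- n = 63: 1.999 / 7.937 = 0.25 SD of change.

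A change of that size passes the test whatever caused it.

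**The case against.** **The document is terse, and a comparator might exist unreported.** Ethical Consideration says students were treated equally whether or not they took part, so non-participants are mentioned. That sentence is an ethics assurance and describes no measurement of them. The one-group reading does not rest on silence alone: the sample is 70 and all 70 are taught.

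**Quasi-experimental commonly includes one-group before-after studies.** True, so the label is incomplete rather than wrong. It also covers designs with a non-randomised control, and the reader is not told which this is.

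**The claim is modest.** The aim says *explore*, the introduction also speaks of exploring potential impact, and the hypotheses claim only change. This has some force for the aim. It does not soften the title or the introduction's stated intent to investigate effectiveness.

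**A one-group study can give preliminary evidence.** It can describe change, and the within-group hypotheses should stay. It still cannot assign the cause of that change.

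**The figures come from their assumptions.** This stands. They range from under 1% to 91%, and some unpaired entries fall below the nominal 5%. Background change could also be negative and hide a benefit. In addition, the protocol does not say when the three outcome scales were given, so twelve weeks is the length of the programme and not a stated measurement interval. The numbers illustrate the problem; the conclusion does not depend on them.

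**Conclusion.** The concern holds. The design described is a single group in which all 70 students are exposed, and the effectiveness and impact claimed in the title, introduction and aim are beyond what it can show. This follows from the protocol's own sample and group numbers.

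The size of the risk cannot be fixed from the document. Under a paired test and an assumed background change of 0.2 to 0.4 SD of change, an ineffective programme would appear significant in 38% to 91% of studies with 70 students, or 35% to 88% with 63. An unpaired test would give lower figures at the correlations tried.

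This should be fixed, but it does not invalidate the data, which can still describe within-group change.

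**What to change.** - **Title, introduction and Aim of the Study:** replace effectiveness and impact with change from before to after the programme.
- **Research Hypotheses:** keep all three as within-group changes.
- **Research Design:** beside the quasi-experimental label, state that this is a one-group design with no concurrent comparator, and that no change will be attributed to the teaching method.

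The cost is wording and a less favourable claim. Fieldwork ended in March 2023, before the document date of 10-1-2024, so no comparison data or additional students are requested.

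### Does the Learning Attitude Scale reward anxiety because the protocol does not mention reverse scoring?

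*Protocol*

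**What the plan says.** Under Tools of data collection, item (2), the protocol describes the Learning Attitude Scale and credits it to a cited source (reference 28). "The scale consisted of 40 items divided into four subsections", with 9, 11, 10 and 10 items. The last subsection is introduced as "the fourth (10 items), with anxiety about learning, e.g. (I am anxious while being", and the sentence runs on: "introduced a new subject). This tool uses a five-point Likert scale". The anchors and the direction come next: "1 = not at all, 5 = very much), and the higher the score, the better the learning attitude".

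Hypothesis 1, under Research Hypotheses, says that students' learning attitude "will be improved after participating in situation-based FL with gamification classes". The Statistical Design section describes one step before analysis, a completeness check ("And checked to ensure no information was lost or inadequate"). It then names the ANOVA F test and the t-test, and refers to "the analysis of the association between total scores". The protocol does not mention reverse scoring, negatively worded items or separate reporting of the anxiety subsection.

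**The concern.** The anchors and the direction are given for the tool as a whole. Agreeing strongly with the anxiety example is an unfavourable answer, yet it carries the code 5. Read literally, the most anxious student would get the most credit on that item for a good learning attitude.

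The score serves Hypothesis 1. If the before/after comparison uses the 40-item total, which is inferred because the protocol does not say so outright, then any change in unreversed items enters with the wrong sign. A fall in anxiety would hide improvement and a rise would inflate it. If anxiety did not change, the mean change would be unaffected.

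**Working it through.** **Inputs.** From Tools of data collection, item (2): subsections of 9, 11, 10 and 10 items, responses coded 1 to 5, higher meaning better. The protocol gives no SD and no expected shift, so no power figure can be derived. A simple sum score is assumed below.

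**The plan's own figure.** 9 + 11 + 10 + 10 = 40, as stated. A sum score then runs from 40 × 1 = 40 to 40 × 5 = 200, and the anxiety subsection holds 10/40 = 25% of the items.

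**One unreversed item.** A response r scores r instead of 6 - r. The error is r - (6 - r) = 2r - 6, which is -4, -2, 0, +2, +4 for r = 1 to 5.

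**Effect on a before/after change.** Let k items be negatively worded, with mean favourable change b per item. They should add +kb to the change in the total. Unreversed, they add -kb, so the change is understated by 2kb. At an assumed b = 0.5:

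| k | 2kb (points) |
|---|---|
| 1 (the item shown) | 1 |
| 5 (assumed) | 5 |
| 10 (assumed, whole subsection) | 10 |

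**As a share of the true change.** Assume that every other item is positively keyed and that all items shift favourably by d. The raw sum changes by (40 - k)d - kd = (40 - 2k)d instead of 40d:

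| k | Raw change | Share lost |
|---|---|---|
| 1 | 38d | 5% |
| 5 | 30d | 25% |
| 10 | 20d | 50% |

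The positive-keying assumption is itself doubtful. The first subsection's example ("the first (9 items), dealt with the nature of learning, e.g. (the clever ones learn more easily") has no clear favourable direction.

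**Extreme case.** Suppose all ten anxiety items are worded like the example and a student scores 5 on the other 30 (150 points). The raw sum is 150 + 10 = 160 with no anxiety and 150 + 50 = 200 with maximum anxiety. With reversal the totals are 200 and 160. The ranking flips, with a 40-point swing.

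**Which reading fits the text?** The arithmetic matters only if raw codes are summed, so the two readings of the scale description need comparing.

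- *Raw codes summed.* The anchors hold, but the stated direction fails for the anxiety item.
- *Negative items reversed, then summed.* The anchors still describe what the student marks, and the stated direction holds for the scored total.

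The description does not say that the marked code is the number of points earned, or that codes are added unaltered. Only the second reading makes both statements true. The order of the sentences does not favour the first: the anchors follow the anxiety example because anxiety is the last subsection listed.

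**The case for a change.** The best case for keeping the concern is that the protocol does not merely omit something. It states a response key and a direction for this outcome, and the two do not fit the printed anxiety item unless a further step is taken that is mentioned nowhere. An analysis plan that reversed the items would still leave this description incomplete. Nor does the document offer corroboration. It reports this study's own Cronbach's alpha for the problem-solving scale (0.92) and the empathy scale (0.81), but for learning attitude only the source study's 0.84, although the questionnaire was translated into Arabic.

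Part of this stands. The protocol alone does not tell a reader which items are reversed, or confirm that any were. The arithmetic is also correct on its assumptions.

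The claim of a conflict does not stand. It needs a rule that every marked code counts as points, and the protocol does not state one. Anchors followed by an overall direction are an ordinary way to describe a scale with reverse-keyed items. The missing within-study alpha shows nothing about scoring in either direction. The short Statistical Design section is silent on recoding, but it is silent on nearly all data handling, so little can be inferred from that.

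**Conclusion.** No change to the plan is needed. The protocol fixes the direction of the score and cites the instrument. Honouring both requires an analyst to reverse negatively worded items, and nothing in the text instructs otherwise. The item-by-item reversal list is a detail that normally sits in the scoring key, the syntax or the analysis plan, and the analysis plan is not at hand here.

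The possible effect is real but conditional. If raw codes were summed, the documented exposure is one item, wrong by -4 to +4 points per student. At an assumed favourable shift of 0.5 that is 1 point in the mean change, on a total running from 40 to 200. The losses of 25% and 50% and the 40-point swing rest on unseen items being worded like the example, and the two percentages also on every other item being positively keyed and shifting equally. The link to Hypothesis 1 rests on the inference that the 40-item total is what gets compared.

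This conclusion assumes that the items were scored to match the stated direction. The source key is not available, so the document neither proves that nor shows any mis-scoring.
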